6.3.3 Endometrial Biopsy

Endometrial biopsy will be performed per the provided standard collection method. Samples are to be fixed and stored using directions supplied by the centralized laboratory. The investigator shall do his/her best to obtain endometrial tissue for analysis. The Investigator must record whether tissue was obtained, and send the tissue obtained to the centralized laboratory to be processed.

At the centralized laboratory, a single pathologist will assess the slides from the endometrial biopsies obtained at Screening (per the standardized criteria for determining hyperplasia, as detailed in *Blaustein's Pathology of the Female Genital Tract* (Kurman RJ, 2011) as well as any biopsies obtained if a subject experiences vaginal bleeding while on study drug. Three independent pathologists (from different institutions with independent fiduciary and organizational reporting), blinded to subject's treatment group and to each other's readings, will assess the endometrial biopsies obtained at the Week 12/Early Termination Visit. The concurrence of two of the three pathologists will be accepted as the final diagnosis. If there is no agreement among the three pathologists, the most severe pathologic diagnosis (i.e., atypical hyperplasia > complex hyperplasia > simple hyperplasia > benign endometrium) would be used as the final diagnosis. If hyperplasia is diagnosed by the single safety reader for a subject who has bled while on study drug, this diagnosis be maintained for the efficacy evaluation and the slides become part of the slide set given to the two other pathologists for reading.

Per the draft FDA guidance on estrogen and estrogen/progestin drug products to treat vasomotor symptoms and vulvar and vaginal atrophy symptoms (US Dept. Health and Human Services, 2003), the set of slides distributed to each of these pathologists for the end-of-study pathology review will incorporate control slides representing a randomly selected 10% of the screening normal slides and all slides from subjects excluded for the diagnosis of hyperplasia or cancer to insure quality control.

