6. STATISTICAL METHODOLOGY

6.1 Statistical and Analytical Issues

6.1.1 Statistical Methods

All statistical methods will be based on the International Conference on Harmonization (ICH) E9 document "Statistical Principles for Clinical Trials".

All data will be summarized by treatment group. In addition, where appropriate, a total overall group column will be included to summarize all subjects. Where appropriate, data will be summarized by treatment group and visit.

In summary and analysis tables of continuous variables, the minimum and maximum statistics will be presented to the same number of decimal places as the original data. The mean, median, quartiles, Least Squares mean (LS mean), and 95% Confidence Interval (CI) will be presented to one more decimal place than the original data. The standard deviation (SD) and standard error (SE) will be presented to two more decimal places than the original data. Standard descriptive statistics (number of subjects with data available [n], mean, SD, median, quartiles, minimum and maximum) will be presented in summary tables. The LS mean, SE and 95% CI will be presented in the statistical analysis outputs as appropriate.

In summary tables of categorical variables, the number of non-missing observations and percentages will be presented. The denominator for each percentage will be the number of subjects within the population and treatment group of interest with non-missing responses, unless otherwise specified.

All hypothesis testing will be 1-sided unless otherwise specified and carried out at the 2.5% significance level, designed to evaluate the superiority of estriol vaginal gel versus placebo vaginal gel.

P-values will be rounded to 3 decimal places. P-values less than 0.001 will be reported in the tables as '<0.001'. P-values greater than 0.999 will be reported as '>0.999'.

Should any of the statistical methods proposed prove unsuitable during the final analysis, more appropriate methods will be used and any changes will be documented in the Clinical Study Report (CSR), including the rationale for use.

All data collected on the electronic case report form (eCRF) as well as the data from central laboratories will be presented in data listings. The subject data listings will be sorted by unique subject number, randomized treatment group and visit or visit date, as appropriate. Further sorting variables may be used if required.

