6.4.8 Endometrial Biopsy

An endometrial biopsy is performed in subjects with a uterus as a mandatory procedure at the Screening and Week 12 / Early Termination visits, and whenever the subject presents with vaginal bleeding at any other visit.

The slides from the endometrial biopsies will be sent to the central laboratory, [REDACTED] for evaluation. Three independent pathologists, who will be blinded to subject, treatment assignment and to each other's evaluations, will assess the endometrial biopsies obtained at the Week 12 / Early Termination visit plus 10% of the Screening slides and all slides diagnosed with hyperplasia or cancer. The slides from the Screening visit and from any visit where the subject presents with vaginal bleeding will be assessed by only the primary pathologist.

The primary pathologist will be from [REDACTED] and the other two pathologists will be from different institutions but will travel to [REDACTED] to evaluate the endometrial biopsies.

Each pathologist will provide their evaluation according to the following categories, which are ordered from best to worst diagnosis, i.e. atypical hyperplasia (carcinoma) is the most severe diagnosis, followed by complex hyperplasia, simple hyperplasia and benign endometrium accordingly.

Table 5: Histologic Characteristics of the Endometrium

0	No tissue
1	Tissue insufficient for diagnosis
2	Atrophic
3	Inactive
4a	Weakly proliferative
4b	Active proliferative
4c	Disordered proliferative
5a	Secretory - Cyclic type
5b	Secretory - Progestational type (including stromal decidualization)
6	Menstrual type
7	Simple hyperplasia without atypia
8	Simple hyperplasia with atypia
9	Complex hyperplasia without atypia
10	Complex hyperplasia with atypia
11	Carcinoma (specify type)

For any subject, the final diagnosis will be accepted as the concurrence of two of the three pathologists. If there is no agreement among the three pathologists, the most severe pathologic diagnosis will be used as the final diagnosis. The evaluations of all three pathologists must be verified by the CRA in order to be considered for final analysis.

If hyperplasia is diagnosed by the single safety reader for a subject who has bled while on study treatment, this diagnosis will be maintained for the efficacy/safety evaluation and the slides become part of the slide set given to the two other pathologists for reading.

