The bullet points below specify how many pathologists will review the biopsy samples at each visit and how the final diagnosis of a sample will be programmatically derived at each visit.

- Screening Visit
 - Biopsy sample is mandatory.
 - Samples reviewed by Pathologist 1 only.
 - Final diagnosis = diagnosis of Pathologist 1
 - 10% of samples will also be reviewed by Pathologist 2 and Pathologist 3 **for QC purposes only**. The diagnoses of Pathologist 2 and Pathologist 3 will **not** be used in the determination of final diagnosis.

- All slides diagnosed with hyperplasia or cancer (categories 7, 8, 9, 10 or 11 from Table 5 above) by Pathologist 1 will also be reviewed by Pathologist 2 and Pathologist 3 **for QC purposes only**. The diagnoses of Pathologist 2 and Pathologist 3 will **not** be used in the determination of final diagnosis.
- Baseline, Week 3 and Week 8 Visits
 - Biopsy sample is only taken if the subject presents with vaginal bleeding at the visit, otherwise the eCRF is marked as Not Applicable.
 - Samples reviewed by Pathologist 1 only.
 - Final diagnosis = diagnosis of Pathologist 1
 - All slides diagnosed with hyperplasia or cancer (categories 7, 8, 9, 10 or 11 from Table 5 above) by Pathologist 1 will also be reviewed by Pathologist 2 and Pathologist 3 **for QC purposes only**. The diagnoses of Pathologist 2 and Pathologist 3 will **not** be used in the determination of final diagnosis.
- Week 12 / Early Termination Visit
 - Biopsy sample is mandatory.
 - Samples reviewed by Pathologist 1, Pathologist 2 and Pathologist 3.
 - Final diagnosis derived as follows:
 - If the subject presents with vaginal bleeding at the visit (as indicated by an answer of 'Yes' to the direct question on the eCRF) and Pathologist 1 diagnoses hyperplasia or cancer (categories 7, 8, 9, 10 or 11 from Table 5 above):
 - Final diagnosis = diagnosis of Pathologist 1, **regardless** of the diagnoses of Pathologist 2 and Pathologist 3, even if Pathologist 2 and Pathologist 3 concur on a different diagnosis, either more or less severe than that of Pathologist 1.
 - Otherwise:
 - If two of the three pathologists agree (i.e. diagnose the same category from Table 5 above), their agreed diagnosis is the final diagnosis.
 - If all three pathologists diagnose a different category from Table 5 above), the most severe diagnosis is taken as final diagnosis.

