For summary purposes, the Baseline histologic result will be the final diagnosis from the Baseline visit if endometrial samples were taken due to the subject presenting with vaginal bleeding at that visit, or the final diagnosis from the Screening visit otherwise.

The number and percentage of subjects with each histologic characteristic will be summarized (according to the final diagnosis, as defined above) at each visit by treatment group and overall.

A table presenting the shift in result from Baseline to Week 12 / Early Termination (according to the final diagnosis) will also be presented by treatment group. For the shift table, the denominator of percentage will be the number of subjects in the Safety population in each treatment group.

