Table 14.3.5.2	Summary of Shifts from Baseline to Week 12 / Early Termination for Transvaginal Ultrasound Assessments	Safety Population
Table 14.3.6.1	Summary of Endometrial Biopsy Histologic Characteristics by Treatment and Visit	Safety Population
Table 14.3.6.2	Summary of Shifts from Baseline to Week 12 / Early Termination for Endometrial Biopsy Histologic Characteristics	Safety Population
Table 14.3.7.1	Summary of 12-Lead Electrocardiogram Parameters by Treatment and Visit	Safety Population
Table 14.3.7.2	Summary of 12-Lead Electrocardiogram Overall Interpretation by Treatment and Visit	Safety Population
Table 14.3.8	Summary of Vital Signs by Treatment and Visit	Safety Population
Table 14.3.9	Summary of Physical Examination by Treatment and Visit	Safety Population
Table 14.3.10	Summary of Gynecological Examination by Treatment and Visit	Safety Population

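### At Week 12 the SAP treats two matching non-diagnostic biopsy codes as an agreed diagnosis, so a lone hyperplasia or carcinoma reading can be tabulated as non-diagnostic

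*SAP*

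**What the plan says.** Protocol 6.3.3 has three blinded, independent pathologists read the Week 12 / Early Termination biopsies. Its rule is: "The concurrence of two of the three pathologists will be accepted as the final diagnosis". Without agreement the most severe diagnosis is used, on a scale from atypical hyperplasia down to benign endometrium.

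SAP 6.4.8 turns this into a programmed derivation. If the woman is bleeding at the visit and Pathologist 1 reads category 7 to 11 (hyperplasia or carcinoma), that reading is final. Otherwise two bullets apply:

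- The first bullet covers a match between readers: "If two of the three pathologists agree (i.e. diagnose the same category from Table 5 above), their agreed diagnosis is the final diagnosis". It makes no exception for any category.
- The second bullet brings in severity, but only where no two readings match: "If all three pathologists diagnose a different category from Table 5 above), the most severe diagnosis is taken as final diagnosis".

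Table 5, to which both bullets refer, has 15 categories. The first two are 0, no tissue, and 1, "Tissue insufficient for diagnosis". The section also requires that "The evaluations of all three pathologists must be verified by the CRA in order to be considered for final analysis".

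The final diagnosis feeds Table 14.3.6.1, "Summary of Endometrial Biopsy Histologic Characteristics by Treatment and Visit", and the shift table 14.3.6.2. For the latter, "For the shift table, the denominator of percentage will be the number of subjects in the Safety population in each treatment group".

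**The concern.** Codes 0 and 1 record that a reader could not make a diagnosis. The first bullet lets two such codes, if they match, count as the agreed diagnosis and outvote the one reader who did make one. If the two codes differ, the second bullet applies and the lone diagnosis stands. The diagnostic evidence is the same in both cases, one diagnosis and two failures to diagnose, yet the results are opposite.

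The matching-code result is also the less cautious one, whereas both documents choose the most severe diagnosis when readers do not agree. Change in endometrial histology at Week 12 is a listed safety endpoint (Protocol 7.4), and Protocol section 1 names endometrial tumors among the primary risks of estrogens. At stake is whether a lone finding of hyperplasia or carcinoma appears in the by-arm tables or is shown there as a non-diagnostic biopsy.

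**Working it through.** The plan states no figure for this point, so the check is to apply the rule literally to every combination of readings.

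**Inputs.** SAP 6.4.8, Table 5: 15 categories (0, 1, 2, 3, 4a, 4b, 4c, 5a, 5b, 6, 7, 8, 9, 10, 11). Two are non-diagnostic (0, 1), eight are benign diagnoses (2 to 6) and five are hyperplasia or carcinoma (7 to 11). Three readers.

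**Examples**, in the order Pathologist 1, 2, 3:

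| Readings | Final, no bleeding | Final, bleeding at visit |
|---|---|---|
| 1, 1, 10 | 1 | 1 |
| 10, 1, 1 | 1 | 10 |
| 0, 1, 10 | 10 | 10 |
| 2, 2, 10 | 2 | 2 |

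The last row is ordinary two-of-three voting between diagnoses and is not in dispute.

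**Patterns with one reading in 7 to 11 and two in {0, 1}.**

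- All such patterns: 3 positions × 5 categories × 2 × 2 codes = 60, out of 15³ = 3,375 ordered triples.
- Matching codes: 3 × 5 × 2 = 30 (15 with 0, 0 and 15 with 1, 1). Without bleeding, all 30 end non-diagnostic.
- Differing codes: 60 − 30 = 30. All end as hyperplasia or carcinoma.
- With bleeding, the exception rescues the matching patterns in which Pathologist 1 is the lone reader: 5 × 2 = 10. The other 30 − 10 = 20 still end non-diagnostic.

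These counts show which patterns are affected. They are not probabilities.

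**Effect of two possible remedies, without bleeding.**

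- Removing codes 0 and 1 from the vote whenever any reader makes a diagnosis changes every pattern with two matching non-diagnostic codes and one diagnosis: 3 × 13 × 2 = 78. Of these, 30 gain a hyperplasia or carcinoma result. The other 3 × 8 × 2 = 48 turn a two-reader non-diagnostic result into a benign diagnosis on one reader, for example 1, 1, 2 becoming 2.
- Protecting only a lone reading of 7 to 11 changes the 30 and leaves the 48 alone. With bleeding it changes 20.

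**Size of one case.** 280/4 = 70 women per arm. If all are dosed, one case is 1/70 = 1.4% of an arm in the shift table.

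**The case against.** The case for leaving the rule alone has several parts.

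*It follows the protocol.* Two-of-three concurrence is the protocol's rule, and two blinded experts agreeing that tissue is inadequate is a substantive judgement. This stands in part: it is a good reason not to let one reader turn an inadequate biopsy into a benign one. It is weaker for a lone hyperplasia or carcinoma reading. The protocol speaks of concurrence on a diagnosis, and its severity scale names neither non-diagnostic code.

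*A sensible programmer would not count 0 and 1 as diagnoses.* On that reading, 1, 1, 10 is not agreement, and the general sentence in SAP 6.4.8 on non-agreement would give 10. But the bullets that specify the programmed derivation define agreement as the same Table 5 category and reserve the severity rule for three different categories. If 0 and 1 are not diagnoses, 1, 1, 10 fits neither bullet. The text needs correcting on either reading.

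*The case is rare.* This stands. Two readers seeing no tissue while a third diagnoses hyperplasia is hard to credit, so half of the 30 matching patterns carry little weight. The 1, 1 pattern is more plausible, but the documents give no rate for it.

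*Nothing is hidden.* This also stands. A reader might infer that the plan suppresses hyperplasia findings. The documents do not support that: SAP 6.1.1 says eCRF data "as well as the data from central laboratories will be presented in data listings", and Listing 16.2.10 is dedicated to the biopsies. Only the summary and shift tables lose the reading.

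**Conclusion.** The point holds in a narrow form. On the literal text of SAP 6.4.8, a lone Week 12 / Early Termination reading of category 7 to 11 is reported as non-diagnostic in Tables 14.3.6.1 and 14.3.6.2 when the other two readers give the same non-diagnostic code. The exception is a woman bleeding at the visit with Pathologist 1 as the lone reader. With differing codes the same reading is kept.

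The size is small. No hypothesis test or efficacy conclusion depends on this endpoint, the event is likely rare, and its frequency cannot be estimated from the documents. The 1.4% is what one case would amount to, not an expected effect, and it assumes 70 dosed women per arm.

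Two stronger inferences should be resisted. The 30 of 60 patterns do not mean that half of such cases would be lost, because the count reflects only how many codes Table 5 has. Nor does the point show that non-diagnostic codes should never prevail: a majority non-diagnostic result against a lone benign reading is a defensible choice. The rule is still worth correcting, since a safety classification should not turn on whether two readers used the same code for a failed sample.

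**What to change.** Keep the bleeding exception, the CRA verification requirement and two-of-three voting between diagnoses. In SAP 6.4.8, Week 12 / Early Termination, add as the first step of the *Otherwise* branch, ahead of the agreement bullet:

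*If one pathologist gives a category from 7 to 11 and the other two give category 0 or 1, matching or not, the category from 7 to 11 is the final diagnosis.*

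Leave a majority non-diagnostic result with a lone benign reading, such as 1, 1, 2, as it is now. Footnote Tables 14.3.6.1 and 14.3.6.2 with the number of final hyperplasia or carcinoma diagnoses per arm that rest on one diagnostic reading.

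The cost is one sentence, one programming branch and one footnote before unblinding, with no new slide readings. The downside is that an occasional final diagnosis of hyperplasia or carcinoma rests on one reader. That errs on the side of safety, and the footnote discloses it.

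### The endometrial shift table sets a one-reader Baseline diagnosis against a three-reader Week 12 diagnosis, so within-arm shifts can be biased in a direction not known in advance; a same-reader table should be added.

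*SAP*

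**What the plan says.** **Baseline.** Protocol 6.3.3 provides that "a single pathologist will assess the slides from the endometrial biopsies obtained at Screening". SAP 6.4.8 repeats this for the Screening Visit ("Samples reviewed by Pathologist 1 only") and sets "Final diagnosis = diagnosis of Pathologist 1". Pathologists 2 and 3 re-read 10% of Screening samples and all slides that Pathologist 1 calls hyperplasia or cancer, for quality control only. The Baseline value for summaries is the Baseline-visit diagnosis if a biopsy was taken for bleeding, "or the final diagnosis from the Screening visit otherwise". In both cases it is one reading by Pathologist 1.

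**Week 12/Early Termination.** "Samples reviewed by Pathologist 1, Pathologist 2 and Pathologist 3". The rule is then: "If two of the three pathologists agree (i.e. diagnose the same category from Table 5 above), their agreed diagnosis is the final diagnosis". In a three-way split, "the most severe diagnosis is taken as final diagnosis". There is one exception: if the woman is bleeding at the visit and Pathologist 1 reads hyperplasia or cancer, Pathologist 1's reading stands.

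**Shift table.** "A table presenting the shift in result from Baseline to Week 12 / Early Termination (according to the final diagnosis) will also be presented"; this is Table 14.3.6.2 in SAP 7.2.3, split by arm. No shift based on the same reader at both visits is planned.

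**The concern.** Change from Baseline in endometrial histology at Week 12 is a listed safety endpoint (Protocol 7.4), and Table 14.3.6.2 is the only shift display planned for it. For an estrogen product, movement among the benign categories, such as atrophic or inactive to proliferative, is a large part of what such a table is read for. Its two sides follow different rules, so women whose endometrium has not changed can still move.

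Two forces act at Week 12 and not at Baseline:

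- The majority step discards isolated readings, high or low.
- The most-severe step pushes upward, but only when all three readers differ.

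The SAP's level of detail makes three-way disagreement more likely. Protocol 6.3.3 orders severity on four levels with all benign endometrium in one. The SAP requires agreement on the exact category out of the 15 in Table 5. Readings of atrophic, inactive and weakly proliferative are all benign on the protocol's order, but in the SAP they count as a three-way disagreement and resolve to weakly proliferative.

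At stake is the within-arm statement: an apparent estrogenic shift that is not there, or a real one partly masked.

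**Working it through.** The plan states no figure on this point, so there is none to reproduce. Reader error rates are not in the documents and are assumptions throughout.

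**Exact enumeration, three categories in use.** Each reader independently gives the low, middle or high category with probabilities p1, p2, p3, the same at both visits (no true change).

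- Majority for category j: m_j = 3·p_j²·(1 − p_j) + p_j³
- All three differ: A = 6·p1·p2·p3
- Week 12 distribution: w1 = m1, w2 = m2, w3 = m3 + A
- Up = p1·(w2 + w3) + p2·w3; Down = p2·w1 + p3·(w1 + w2); Net = Up − Down
- Pathologist 1 at both visits: Up = Down = p1·(p2 + p3) + p2·p3

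*Upward example*, true category in the middle, .1/.8/.1: A = 6 × .1 × .8 × .1 = .048; w = .028, .896, .028 + .048 = .076. Up = .1 × .972 + .8 × .076 = .158. Down = .8 × .028 + .1 × .924 = .115. Net +4.3 points.

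*Downward example*, true category the lowest in use, .8/.15/.05: A = .036; w = .896, .061, .043. Up = .8 × .104 + .15 × .043 = .090. Down = .15 × .896 + .05 × .957 = .182. Net −9.3 points (from unrounded values).

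| Low/mid/high | All differ | Up | Down | Net (points) | Same reader, each way |
|---|---|---|---|---|---|
| .1/.8/.1 | 4.8% | 15.8% | 11.5% | +4.3 | 17.0% |
| .2/.6/.2 | 14.4% | 32.8% | 21.3% | +11.5 | 28.0% |
| .3/.4/.3 | 21.6% | 40.8% | 25.7% | +15.1 | 33.0% |
| .9/.08/.02 | 0.9% | 2.6% | 9.8% | −7.2 | 9.2% |
| .8/.15/.05 | 3.6% | 9.0% | 18.2% | −9.3 | 16.8% |
| .7/.2/.1 | 8.4% | 17.4% | 24.6% | −7.2 | 23.0% |
| .6/.3/.1 | 10.8% | 25.2% | 28.1% | −2.9 | 27.0% |
| .5/.3/.2 | 18.0% | 33.5% | 29.3% | +4.2 | 31.0% |

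In the first three rows the true category is in the middle. In the rest it is the lowest, so errors go only upward; they inflate the single Baseline reading and are outvoted at Week 12.

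**Simulation over case mix.** Five categories, 400,000 women per scenario, reader error SD 0.5 to 1.0 category, error correlation between readers 0 or 0.5:

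- 70% of women truly in the lowest category: net −3.6 to +1.0 points
- 50% in the lowest: −1.2 to +5.6
- mid-scale mix: +1.2 to +17.0

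**Systematic reader differences.** With 70% in the lowest category, SD 0.7 and no correlation, if Pathologists 2 and 3 read 0.3 category higher than Pathologist 1 the net is +10.9 points. If they read 0.3 lower it is −12.0.

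**Same reader at both visits.** The net shift is zero in every exact scenario and within ±0.2 points in simulation.

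**Price of a single reader.** Total false shifts at .1/.8/.1 are 15.8 + 11.5 = 27.3% under the plan and 2 × 17.0 = 34.0% with one reader. At .2/.6/.2 they are 54.1% and 56.0%. At .3/.4/.3 the advantage is gone: 66.5% and 66.0%.

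**Scale.** If all 70 women planned per arm had a uterus and both biopsies, which is an upper limit, +4.3, −9.3 and +15.1 points correspond to about 3 up, 6 to 7 down and 11 up, net.

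**The case against.** The structure is deliberate. Protocol 6.3.3 prespecifies one reader at Screening, three at the end, majority, then most severe, and the SAP carries that through. Taking the worst reading in a three-way split is a conservative safety convention, not an error. The table is descriptive, and SAP 7.4.5 plans an endometrial biopsy listing. All of this stands, and none of it makes the two sides of the table comparable.

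A reader might infer three stronger things that the documents do not support:

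- **That the table must show worsening.** The most-severe step acts only when all three differ. The women are postmenopausal, and hyperplasia, cancer and other endometrial pathology are excluded at entry (Protocol 4.1.2). A concentration at the low end of Table 5 is therefore plausible, and there the artefact can be an apparent improvement. Hyperplasia appearing where Baseline had none also follows from the entry exclusion under any reading rule.
- **That it creates a false difference from placebo.** The Week 12 readers are blinded to treatment and one rule applies to all arms. With no true change in any arm, the expected artefact is the same in each.
- **That the planned table should be replaced.** A single-reader table has more false shifts at moderate error rates. It would also omit a Week 12 hyperplasia called by Pathologists 2 and 3 but not by Pathologist 1, so two safety tables would disagree.

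**Conclusion.** The point holds for within-arm shifts. Different reading rules at the two visits can give a spurious net shift with no true change. Its sign and size depend on reader error, case mix and reader differences, none of which the documents give.

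Exact enumeration under the assumed error rates spans about −9 to +15 points, and the simulated mid-scale mix reaches +17.0. A systematic reader difference of 0.3 category gives about −12 or +11. These are illustrations over assumed ranges, not estimates for this trial. They assume identical error behaviour at both visits, and they leave out the bleeding exception at Week 12 and the entry exclusion.

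The effect does not by itself bias the comparison with placebo. The point is a cheap improvement, not a flaw that threatens the safety conclusion.

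**What to change.** In SAP 6.4.8:

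1. Keep the planned shift table, and keep the three-reader final diagnosis for all hyperplasia and carcinoma counts.
2. Add a supplementary shift table by treatment group using Pathologist 1's reading at both visits. Label it as a same-reader comparison for interpreting within-arm shifts.
3. Report, by arm, how often all three readers differed at Week 12/Early Termination, since only then does the most-severe step apply.

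Cost: SAP wording, one more table and one count. Pathologist 1 already reads every Screening and every Week 12/Early Termination slide, so no extra slides, readers or readings are needed. The added table removes the change of rule and differences between readers. It does not remove the effect of the entry exclusion or any drift in Pathologist 1's own reading over time, and it carries more random misclassification at moderate error rates. That is why it belongs beside the planned table and not in its place.
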